## f) Procedures Involved in the Human Research

Every patient's dystonic movement disorder will be videotaped at each time point. The patient will bring in their instrument if possible; a keyboard will be provided for pianists. The patient will be encouraged to wear similar clothing/jewelry/nail polish etc. so each video recording will be identical at each time point.

The study will last a total of 24-28 weeks with the schedule as follows:

Visit 1- (Day 0) - Screening and baseline:

- Consent Form Process – completed prior to any research procedures
- Comprehensive Neurologic History and Physical Examination (MRC scales and dynamometry)
- Blood tests
- Patient's subjective rating scale of symptoms at baseline, HADS and perceived stress (questionnaires)
- Video of targeted hand(s) by [name] at NYU Langone medical center
- Selection of Muscles to inject – by [name] at NYU Langone medical center.
- Identification of the muscles and Injection of muscles

Visit 2 and Visit 3 will contain the following evaluations:

- Brief neurological exam to evaluate for weakness of the targeted muscles and surrounded non-targeted muscles (dynamometry, and MRC )
- Patient's subjective rating scale of symptoms, HADS and perceived stress (questionnaires)
- Assess for side effects
- Video of targeted hand(s) by [name] at NYU Langone medical center.
- Administer booster to patients who feel symptoms have not improved

Visit 4

 Mount Sinai	Protocol Title:	A PLACEBO-CONTROLLED, DOUBLE-BLIND, RANDOMIZED, CROSS OVER PILOT STUDY OF THE EFFICACY AND TOLERABILITY OF INCOBOTULINUM TOXIN A (XEOMIN) AS A TREATMENT FOR FOCAL TASK-SPECIFIC DYSTONIA OF THE MUSICIAN'S HAND
	Principal Investigator Name/Contact Info:	[name].
	Primary Contact Name/Contact Info	[name] [contact]
	Date Revised:	10/22/2019
	Study Number:	HS: 13-00822 GCO: 13-1679

- Brief neurological exam to evaluate for weakness of the targeted muscles and surrounded non-targeted muscles (dynamometry, MRC)
- Patient's subjective rating scale of symptoms, HADS and perceived stress (questionnaires)
- Assessment of side effects
- Video of targeted hand(s) Injection of muscles by [name] at NYU Langone medical center.

Visit 4a or 4b. This is optional visit at Week 6, 8 are depending on optimal dosing at weeks 2 and 4.

This visit will assess the improvement in musical performance. It will be 4 weeks after optimal booster injection.

- Brief neurological exam to evaluate for weakness of the targeted muscles and surrounded non-targeted muscles (dynamometry, and MRC )
- Patient's subjective rating scale of symptoms and perceived stress (questionnaires)
- Assess for side effects
- Video of targeted hand(s) by [name] at NYU Langone medical center.

Visit 5; Week 12 (week 14 or 16 depending on previous dosing schedule) will contain the following evaluations:

- Brief neurological exam to evaluate for weakness of the targeted muscles and surrounded non-targeted muscles (dynamometry, and MRC )
- Patient's subjective rating scale of symptoms, HADS and perceived stress (questionnaires)
- Assess for side effects
- Video of targeted hand(s) (Groups 1 & 2 will be crossed over and will receive their 2nd injection cycle) by [name] at NYU Langone medical center.
- Treatment may be deferred for up to 2-4 weeks in any individuals who have persistent weakness from the first treatment cycle

 Mount Sinai	Protocol Title:	A PLACEBO-CONTROLLED, DOUBLE-BLIND, RANDOMIZED, CROSS OVER PILOT STUDY OF THE EFFICACY AND TOLERABILITY OF INCOBOTULINUM TOXIN A (XEOMIN) AS A TREATMENT FOR FOCAL TASK-SPECIFIC DYSTONIA OF THE MUSICIAN'S HAND
	Principal Investigator Name/Contact Info:	[name].
	Primary Contact Name/Contact Info	[name] [contact]
	Date Revised:	10/22/2019
	Study Number:	HS: 13-00822 GCO: 13-1679

Visit 6 and visit 7; Week 14 or 16 or 18 depending on previous dosing schedule will contain the following evaluations:

- Brief neurological exam to evaluate for weakness of the targeted muscles and surrounded non-targeted muscles (dynamometry, and MRC )
- Patient's subjective rating scale of symptoms, HADS and perceived stress (questionnaires)
- Assess for side effects
- Video of targeted hand(s) by [name] at NYU Langone medical center
- Administer booster to patients who feel symptoms have not improved

Visit 7a or 7b is optional visit which will be 4 week after optimal dosing injection.

- Brief neurological exam to evaluate for weakness of the targeted muscles and surrounded non-targeted muscles (dynamometry, and MRC )
- Patient's subjective rating scale of symptoms, HADS and perceived stress (questionnaires)
- Assess for side effects
- Video of targeted hand(s) by [name] at NYU Langone medical center

Visit 8 Final follow-up evaluation, this visit will be 12 weeks after optimal dosing injection which will be week 24 or 26 or 28

- Brief neurological exam to evaluate for weakness of the targeted muscles and surrounded non-targeted muscles (dynamometry, and MRC )
- Blood Tests
- Patient's subjective rating scale of symptoms, HADS and perceived stress (questionnaires)
- Final assessment for side effects
- Video tape targeted hand(s). This will occur at [name] office at NYU Langone Medical Center. Participants will be referred for clinical care.

Rating at the completion of the study:

 Mount Sinai	Protocol Title:	A PLACEBO-CONTROLLED, DOUBLE-BLIND, RANDOMIZED, CROSS OVER PILOT STUDY OF THE EFFICACY AND TOLERABILITY OF INCOBOTULINUM TOXIN A (XEOMIN) AS A TREATMENT FOR FOCAL TASK-SPECIFIC DYSTONIA OF THE MUSICIAN'S HAND
	Principal Investigator Name/Contact Info:	[name].
	Primary Contact Name/Contact Info	[name] [contact]
	Date Revised:	10/22/2019
	Study Number:	HS: 13-00822 GCO: 13-1679

1. Patient rater (self): Will provide a subjective self-assessment score of symptom improvement in questionnaire form at every visit. They will also be asked to rate their recorded video performances that will be presented to them in a random order.
2. Musician rater: A professional musician (of similar genre) will review the recorded performances in random order and will be asked to rate performance and presence of dystonia.
3. Neurologist rater: Will review the recorded performances in random order and asked to rate dystonia and performance.

Participants will be asked to abstain from getting pregnant during the study treatment period. Women who are of child bearing potential will have a pregnancy test prior to each visit which has an injection. Participants (men and women) will be asked to maintain birth control throughout the study period and their choice of birth control will be noted in the source documents.

Should a subject become pregnant during the study treatment period, study treatments will be discontinued and the pregnancy will be reported as an unexpected AE to the IRB. Pregnancies and their follow-up will be monitored by the study team and reported to the sponsor and the IRB. The pregnancy follow-up will include the outcome of the pregnancy.

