## Brief Summary of Research (250-400 words):

The investigational drug being studied in this protocol is Incobotulinumtoxin A (Xeomin®). Botulinum toxin (BoNT) prevents the release of the acetylcholine from peripheral nerves, inhibiting muscle contractions. BoNT is effective in relaxing overactive muscles. In musician's dystonia, the ability to reduce abnormally overactive muscles in the hand can be critical for the musical professional to continue his or her career. With the use of EMG/electrical stimulation and/or ultrasound guidance, the injector can precisely localize the individual muscles that are affected in this condition with great accuracy. Prior studies have shown that BoNT injections produce beneficial effects in forearm muscles, and less effect in shoulder or proximal arm muscles.

Possible risks in treating patients with BoNT include excessive weakness of the injected muscles. The drug may also affect non-targeted muscles. However these risks will be minimized during the screening period by carefully targeting the affected muscles and by administering low doses of BoNT. Small booster doses may be given at follow up visit (2, 4, 14 and 16-weeks after the primary injection date) if the initial injection was insufficient to produce sufficient efficacy in relief of the focal dystonia and did not produce excess weakness of the targeted muscle.

 Mount Sinai	Protocol Title:	A PLACEBO-CONTROLLED, DOUBLE-BLIND, RANDOMIZED, CROSS OVER PILOT STUDY OF THE EFFICACY AND TOLERABILITY OF INCOBOTULINUM TOXIN A (XEOMIN) AS A TREATMENT FOR FOCAL TASK-SPECIFIC DYSTONIA OF THE MUSICIAN'S HAND
	Principal Investigator Name/Contact Info:	[name].
	Primary Contact Name/Contact Info	[name] [contact]
	Date Revised:	10/22/2019
	Study Number:	HS: 13-00822 GCO: 13-1679

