#### **d) Study Timelines**

There will be 7 or 10 visits depending on which week would be your optimal dosing over the 24-28 week study period. Patients will be seen at weeks 1, 2, 4, 12, 14, 16, and 24, (see attached flow sheet – appendix 1). If patient needs booster dosage at week 2 or 4, patient will be asked to return to have another visit at 4 week after optimal dosing. There will be a total of 7-10 research visits over a 24-28 week period. All visits are expected to last approximately 2-3 hours. The study started in January 2014 and anticipates ending in June 2020. During the study, we may split Visits so that the patient can be seen easily by [name] and not create a hardship for the participant. If the study visit is split, it will mean that [name] assessment will occur prior to the assessment and treatment at [name] location on two consecutive days.

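### Visit 4 lists an injection with no week and without the protocol's own condition for repeat doses, and the visit numbers do not map cleanly to the stated weeks

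*Combined protocol and SAP*

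**What the plan says.** Section 5f opens cycle 1 at Visit 1 (Day 0) with "Identification of the muscles and Injection of muscles". For Visits 2 and 3 it has a conditional step: "Administer booster to patients who feel symptoms have not improved". The Visit 4 list then contains "Video of targeted hand(s) Injection of muscles", with no week beside the visit and no condition on the injection. An optional Visit 4a or 4b follows at week 6 or 8, four weeks after the booster. Cycle 2 opens at "Visit 5; Week 12 (week 14 or 16 depending on previous dosing schedule"), and Visits 6 and 7 carry the same conditional booster step as Visits 2 and 3.

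The Brief Summary of Research restricts repeat dosing in time and by condition. On time: "Small booster doses may be given at follow up visit (2, 4, 14 and 16-weeks after the primary injection date"). On condition, the initial injection must have been "insufficient to produce sufficient efficacy in relief of the focal dystonia and did not produce excess weakness of the targeted muscle".

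Section 5d, Study Timelines, says: "Patients will be seen at weeks 1, 2, 4, 12, 14, 16, and 24". It ties an additional visit to a booster in cycle 1 ("If patient needs booster dosage at week 2 or 4"), gives a total of 7-10 visits, and refers to a flow sheet in appendix 1.

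**The concern.** Section 5f uses two forms of words for dosing: one for an injection that everyone receives (Visit 1) and one for a booster that depends on the patient's response (Visits 2, 3, 6 and 7). Visit 4 follows the first form. A reader working from the visit list alone would find nothing there that limits the injection to patients who still need one and are not weak. The Brief Summary imposes both limits.

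Two things are at stake. The first is who is injected, since excess weakness is a main risk that the protocol names. The second is the crossover comparison. If cycle 1 contains an injection that cycle 2 lacks, patients given BoNT first get a different active regimen from those given BoNT second. Efficacy and weakness under BoNT could then differ between sequences because of the schedule rather than the drug.

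**Working it through.** **1. The plan's own visit count.** Section 5d states 7-10. Section 5f numbers Visits 1 to 8. Assume at most one optional visit per cycle (4a or 4b; 7a or 7b).

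- All numbered visits counted: 8 to 8 + 2 = 10.
- One numbered visit (Visit 4) left out: 7 to 7 + 2 = 9.

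Neither count gives 7-10.

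**2. Visits against weeks.** Section 5d lists seven weeks for eight numbered visits. Two mappings are plausible. In A, Visit 1 is Day 0 and the seven weeks are Visits 2 to 8. In B, the listed week 1 is Visit 1, so that Visits 2 and 3 fall on the cycle 1 booster weeks.

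| Visit | Printed in 5f | Mapping A | Mapping B |
|---|---|---|---|
| 1 | Day 0 | Day 0 | week 1 |
| 2 | none | week 1 | week 2 |
| 3 | none | week 2 | week 4 |
| 4 | none | week 4 | no listed week |
| 5 | week 12 (14 or 16) | week 12 | week 12 |
| 6 and 7 | week 14, 16 or 18 | weeks 14, 16 | weeks 14, 16 |
| 8 | week 24, 26 or 28 | week 24 | week 24 |

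**3. Each mapping against the Brief Summary.**

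- A: Visit 4 falls in a permitted booster week, but its injection lacks the required condition. The Visit 2 booster falls at week 1, which is not among weeks 2, 4, 14 and 16.
- B: the Visit 2 and 3 boosters fall in permitted weeks. Visit 4 has no week in section 5d and no booster window in the Brief Summary.

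**4. Injections per cycle.** Minimum = injections listed without a condition. Maximum = minimum + conditional boosters.

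| Reading | Cycle 1 | Cycle 2 |
|---|---|---|
| Section 5f literally | V1 + V4 = 2; plus V2, V3 = 4 | V5 = 1; plus V6, V7 = 3 |
| Brief Summary weeks and condition govern | 1; plus weeks 2, 4 = 3 | 1; plus weeks 14, 16 = 3 |

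The literal surplus has two sources. The minimum of 2 against 1 comes from Visit 4 alone, under either mapping. The maximum of 4 against 3 comes from Visit 4 under B. Under A, the slot outside the Brief Summary's weeks is Visit 2: if only weeks 2 and 4 count, the occasions are Visits 1, 3, 4 against Visits 5, 6, 7, at most 3 in each cycle.

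**5. Consistency with the crossover date.** The Visit 5 weeks equal 0 + 12, 2 + 12 and 4 + 12. The 12-week interval is stated for Visit 8 and is only inferred here for Visit 5. If every patient were injected at week 4, the week-12 and week-14 options would leave 12 - 4 = 8 and 14 - 4 = 10 weeks. On that inference, the Visit 5 dates assume that some patients receive nothing at week 4, which does not fit an unconditional Visit 4 injection under A.

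**6. Follow-up after Visit 4.** Under A, strength and side effects can be checked at week 8 (the optional visit) and again at Visit 5. Section 5d triggers the optional visit by need for a booster, so a patient injected at Visit 4 without that need has no clear trigger for it. Visit 5 is then the next listed check. Under B, the interval to the next check cannot be dated.

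**The case against.** The strongest reply is that this is a drafting slip. The Visit 4 line reads like two bullets run together, possibly by the text extraction, and the corresponding line at Visits 2, 3, 6 and 7 mentions only the video. Mapping A agrees with every week that section 5f prints, and it puts Visit 4 in a week that both the Brief Summary and section 5d name for boosters. The appendix 1 flow sheet was not among the supplied text and may give the week. Visit 4 starts with an examination for weakness, and section 5i has the assessing physician choose muscles and amounts at each visit, under a stated ceiling of 100 Units.

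Most of this stands, and it rules out several stronger readings that a reader might infer:

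- That the protocol forbids any injection at Visit 4. It does not: a conditional week-4 booster is allowed, and the Visit 5 text is silent on Visit 4.
- That cycle 1 certainly carries an extra injection. This needs section 5f read literally, without the Brief Summary's limits.
- That follow-up after Visit 4 cannot be dated at all. That is true only under mapping B.
- That Visit 4 could be week 12. Visit 5 is printed at week 12, so this is not plausible.
- That patients who already have benefit or weakness will in fact be injected. The safeguards above make this a possibility left open by the wording, not a prediction.

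The reply does not remove the core. The injection wording is present, the condition is absent, and under mapping A the week-1 booster conflicts with the Brief Summary. A flow sheet that supplied the week would leave the conflicting text in place.

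**Conclusion.** The point holds as an internal contradiction. Visit 4 carries an injection with no stated week and without the condition that the Brief Summary sets for repeat doses, and the visit numbers do not map cleanly to the weeks under either plausible mapping.

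Its size depends on which text governs. Read literally, section 5f gives 2 to 4 injections in cycle 1 against 1 to 3 in cycle 2; a patient who needs no booster would get two active injections if given BoNT first and one if given it second. If the Brief Summary's weeks and condition govern, both cycles have 1 to 3 and the imbalance disappears. The documents do not say which prevails.

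The conclusion assumes that the Visit 4 wording is the protocol's own rather than an extraction fault, and that each cycle has at most one optional visit. The sample-size statement does not use the visit schedule and is unaffected. Because the text governs who is injected and whether exposure is equal across the two cycles, the matter is more than clerical.

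**What to change.** The sponsor should reconcile the Brief Summary, section 5d and the visit lists in section 5f, so that they state in the same terms:

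- the week of Visit 4;
- whether an injection belongs to Visit 4 and, if so, under which of the protocol's existing conditions;
- which visits are the booster visits in each cycle, and their weeks;
- a total visit count that matches the numbered and optional visits.

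The appendix 1 flow sheet should be checked against the result. No view is taken on which passage is right. The cost is a wording amendment to the visit list and timeline, with no extra patients or procedures.

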## 1) Objectives:

The research question of this exploratory crossover pilot trial is: compared to placebo, does BoNT significantly improve the motor performance and subjective disability of patients suffering from focal task specific dystonia of the musician's hand? Focal task-specific dystonia of the musician's hand is a disorder that frequently impairs or ends the careers of highly skilled performing artists. [name] has personally evaluated more than 170 of these patients over the last decade; clinically and anecdotally, BoNT is often used to treat these musicians, but few studies exist that quantify their motor and subjective improvement or the prevalence of adverse effects. This trial will be performed using BoNT versus placebo in 20 patients with musician's hand dystonia, to refine quantitative measures of performance using Musical Instrument Digital Interface (MIDI) technology and high speed video analysis, demonstrate efficacy and tolerability of BoNT injections, and provide power calculations for a future multi-center double blind clinical trial.

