#### INCLUSION CRITERIA:

- Patients with focal task-specific dystonia of one or both hands, selectively triggered by performance on a musical instrument.
- Patients must have been evaluated by [name] at the Movement Disorders Division of NYU Langone Hospital as part of their clinical care.
- Patients whose performance on an instrument is directly linked to their occupation.
- Patients must be between the ages of 18 and 80.
- Impairment in musical performance must be visible and demonstrable.

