#### **e) Study Endpoints**

##### **Primary Outcome Measures:**

The principal outcome measure will be improvement in musical performance, measured by self-rated questionnaire, quantitative MIDI analysis and blinded high speed video analysis.

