##### **Secondary Outcomes Measures:**

Patient reported outcomes will be measured by questionnaires that address adverse events; and modified hospital anxiety depression scale (mHADS), and perceived stress scale to capture impact of anxiety, depression and stress.

Motor strength will be tested using the Medical Research Council (MRC) muscle scale and a dynamometer to document any weakness the treatment may produce as compared to the baseline visit.

 Mount Sinai	Protocol Title:	A PLACEBO-CONTROLLED, DOUBLE-BLIND, RANDOMIZED, CROSS OVER PILOT STUDY OF THE EFFICACY AND TOLERABILITY OF INCOBOTULINUM TOXIN A (XEOMIN) AS A TREATMENT FOR FOCAL TASK-SPECIFIC DYSTONIA OF THE MUSICIAN'S HAND
	Principal Investigator Name/Contact Info:	[name].
	Primary Contact Name/Contact Info	[name] [contact]
	Date Revised:	10/22/2019
	Study Number:	HS: 13-00822 GCO: 13-1679

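### The period-1 visit four weeks after optimal dosing (Visit 4a/4b) omits HADS, while its period-2 counterpart (Visit 7a/7b) lists it

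*Combined protocol and SAP*

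**What the plan says.** Section 5(f), on procedures, introduces its visit lists with "The study will last a total of 24-28 weeks with the schedule as follows" and heads several of them with a statement of content, for example "Visit 2 and Visit 3 will contain the following evaluations". There are eight lists: Visit 1, Visits 2 and 3, Visit 4, Visit 4a/4b, Visit 5, Visits 6 and 7, Visit 7a/7b, and Visit 8.

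Two of these are optional visits tied to the optimal injection:

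- **Visit 4a/4b (period 1)** falls at week 6 or 8, four weeks after the optimal booster. Its purpose is given as "This visit will assess the improvement in musical performance". Its questionnaire line names the subjective symptom rating and perceived stress.
- **Visit 7a/7b (period 2)** is also four weeks after the optimal injection. Its questionnaire line names the subjective symptom rating, HADS and perceived stress.

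Section 5(d), Study Timelines, says that a booster at week 2 or 4 leads to a further visit four weeks after optimal dosing. Under Secondary Outcomes Measures, the plan includes the "modified hospital anxiety depression scale (mHADS), and perceived stress scale to capture impact of anxiety, depression and stress". Section 5(f) allows boosters at Visits 2, 3, 6 and 7 for patients who report that symptoms have not improved. The Brief Summary adds the condition that the first injection did not cause excess weakness.

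**The concern.** A two-period crossover gains its precision by comparing each patient's value on one treatment with the same patient's value on the other, at the same time after dosing. Visits 4a/4b and 7a/7b are the matched pair for a patient whose dose was boosted. If a measure is scheduled at one and not at the other, the within-patient difference at that visit cannot be formed for that patient.

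The patients affected are not a random subset. They reach Visit 4a/4b because they were boosted in period 1, and they were boosted because they felt no better. If the drug works, more of them would be expected among those who received placebo first, so the gap could be unequal between the two sequences. A HADS comparison at this visit, restricted to patients with both values, would then describe mainly those who did not need a period-1 booster.

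**Working it through.** The plan states no figure on this point. Its one design figure, 80% power for a difference of 0.935 with within-patient SD 1 and 20 patients, reproduces: the standard error is 1 × √(2/20) = 0.316, and the noncentral t with 18 degrees of freedom gives 79.8%. It concerns an unnamed response variable and does not enter below.

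**Step 1. Questionnaires in each list of section 5(f).**

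| Visit list | Self-rating | HADS | Perceived stress |
|---|---|---|---|
| 1 | yes | yes | yes |
| 2 and 3 | yes | yes | yes |
| 4 | yes | yes | yes |
| 4a/4b | yes | **no** | yes |
| 5 | yes | yes | yes |
| 6 and 7 | yes | yes | yes |
| 7a/7b | yes | yes | yes |
| 8 | yes | yes | yes |
| Total of 8 | 8 | 7 | 8 |

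The only gap is HADS at 4a/4b. Apart from that one word, the questionnaire lines of 4a/4b and 7a/7b agree. The other entries in the two lists (strength tests, side effects, video) are the same.

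**Step 2. What is lost.** Inputs: 20 patients (Objectives, and the statistical paragraph at the end of section 5(h)) and two periods. Let k be the number of patients boosted in period 1; the documents do not give it.

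- HADS scores four weeks after optimal dosing: 20 × 2 = 40.
- Not scheduled at that visit: k, a share of k/40.
- Complete within-patient pairs at that visit: 20 − k.

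| k (assumed) | Scores not scheduled | Pairs left |
|---|---|---|
| 0 | 0 of 40 (0%) | 20 |
| 10 | 10 of 40 (25%) | 10 |
| 20 | 20 of 40 (50%) | 0 |

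The first and last rows are bounds, and the middle row is an illustration. None is an estimate.

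**Step 3. What remains.** HADS is listed at every numbered visit, 1 to 8, so pre-injection and other follow-up scores exist in both periods. Visit 4 also lists HADS, but section 5(f) gives it no week, and two readings are possible:

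- Day 0 plus the seven weeks in Study Timelines (1, 2, 4, 12, 14, 16, 24) makes eight visits and puts Visit 4 at week 4.
- The booster weeks in the Brief Summary (2 and 4) put Visits 2 and 3 at weeks 2 and 4, which leaves Visit 4 undated between weeks 4 and 12.

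On the second reading, Visit 4 might fall near four weeks after a booster. The text therefore shows that HADS is not scheduled at 4a/4b. It does not show that no HADS score exists near that time.

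**The case against.** HADS is a secondary measure, the visit is optional, and no section specifies a between-period HADS comparison at four weeks. The omission looks like a one-word drafting slip, and sites may have given the full questionnaire set anyway. The protocol is dated 10/22/2019 and the study was due to end in June 2020, so a correction helps few patients. All of this stands and limits the size of the point. It does not remove the mismatch: two lists for matched visits differ, and the protocol gives no reason.

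A reader might infer something stronger from the same lists. The principal outcome is "measured by self-rated questionnaire, quantitative MIDI analysis and blinded high speed video analysis", and the Objectives aim "to refine quantitative measures of performance using Musical Instrument Digital Interface (MIDI) technology and high speed video analysis", yet none of the eight lists names a MIDI recording, even at the visit meant to assess musical performance. From that one could conclude that a principal measure was never scheduled. The documents do not support this:

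- Study Timelines refers the schedule to appendix 1 ("see attached flow sheet"), and that sheet was not available for review.
- The lists are not exhaustive. The pregnancy test required before injection visits, stated later in section 5(f), is in none of them.
- The lists also say only video, without the high-speed qualifier, so they do not repeat the endpoint wording in full.

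The silence on MIDI is a reason to ask for clarification. It is not a demonstrated error.

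**Conclusion.** The point holds as a small inconsistency with a cheap remedy. HADS is listed at Visit 7a/7b and not at Visit 4a/4b, although both are set four weeks after optimal dosing. As written, each patient boosted in period 1 loses the paired HADS value at that visit, and the gap depends on response. The size is k of 20 pairs with k unknown. The 50% upper bound on missing scores requires every patient to be boosted in period 1 and should not be read as a forecast.

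This rests on three assumptions: that HADS in the visit lists is the modified scale named among the secondary outcomes; that 7a/7b is the period-2 equivalent of 4a/4b, as the shared timing indicates; and that the lists are followed as written. It does not follow that HADS comparisons between periods are lost altogether. The principal outcome and the sample size calculation are unaffected.

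**What to change.** 1. In section 5(f), make the questionnaire line of Visit 4a/4b the same as that of Visit 7a/7b by adding HADS, for patients who have not yet had the visit. Check that the appendix 1 flow sheet agrees.
2. Before unblinding, list the patients boosted in period 1 who lack a HADS score at 4a/4b. Any HADS comparison at this visit should state how many pairs it uses and that the missing ones arise from booster use.
3. As a clarification only: check the visit lists against the flow sheet for MIDI, and state in the text the device, the visits, and which instruments can yield MIDI data. Eligibility covers dystonia "selectively triggered by performance on a musical instrument" without naming an instrument, and the keyboard provided for pianists is not described as a MIDI device.

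The cost is one short questionnaire at an optional visit, already used at every other visit; a wording change; and one data listing. Scores not taken at past visits cannot be recovered, and the documents do not say whether any are missing.
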